Therapeutic plasma exchange (TPE) offers an immediate and scientifically grounded intervention for the removal of a host of pathogenic antibodies and toxic molecules by centrifugal separation of plasma or plasma membrane filtration. Xiao⁵ and colleagues successfully incorporated TPE in the management of a patient with severe CRS following CAR-T treatment in conjunction with Tocilizumab and steroids with daily documentation of cytokine levels.

Precedence for consideration of TPE in a variety of inflammatory dominant disease states is well known. Interest in adjuvant treatment for management of sepsis and multi organ dysfunction is reflected in Busund⁶ and Rimmer⁷ manuscripts. Patel et al⁸ successfully used TPE in three pediatric patients with pH1N1 influenza A acute respiratory failure and hemodynamic shock despite failure of best supportive care. All three survived with “good functional recovery.”

Ruxolitinib is a JAK/STAT pathway inhibitor which is FDA approved for polycythemia rubra vera, myelofibrosis and graft versus host disease. Kenderion et al⁹ reported a murine model of CRS following CAR-T cellular therapy with marked elevation of IL-6, interferon-gamma, TNF alpha mimicking human CAR-T therapy induced CRS. Ruxolitinib treated mice demonstrated clinical amelioration and decrement in inflammatory cytokines. Incyte Corporation has announced plans to launch a Phase III trial of single agent ruxolitinib for COVID-19 associated cytokine storm.

This protocol will evaluate the efficacy of TPE alone or in combination with ruxolitinib in COVID positive patients with PENN grade 2, 3, 4 CRS. It is hypothesized that dual intervention of acute aphaeretic depletion of cytokines and concomitant suppression of production will produce superior amelioration of the cytokine load and to help to prevent cytokine load rebound. This protocol is envisioned as a pilot study (n=20) for hypothesis generation for future investigation.

Primary Endpoints

1. To document the efficacy of TPE alone or in conjunction with ruxolitinib in decreasing the cytokine load over a 14-day intervention study
2. Analysis of all therapy related adverse events (AEs)

Secondary Endpoints

1. To correlate the clinical course of participants with the degree of specific cytokine reductions
3. To calculate time to independence from mechanical ventilation
4. To calculate time to independence from supplemental oxygen therapy

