5. To measure CRP, ferritin and cytokine levels (IL-6, IL-8, IL-10, TNF α , IFN γ , GM-CSF) to map the cytokine landscape over the course of the study
6. To explore correlative biomarker studies
7. To bank plasma and other blood derivatives in the Prisma Health ITOR Biorepository for future investigation

Study Design

Study type:	Interventional Pilot Clinical Trial
Estimated Enrollment	20 patients
Allocation	Two sequential cohorts, 10 patients per cohort First 10 patients will receive TPE alone (Cohort 1A) Second 10 patients will receive TPE in combination with ruxolitinib
Masking	None (open label)
Primary purpose	Treatment efficacy
Official title:	Interventional Study to Evaluate the Efficacy of Therapeutic Plasma Exchange (TPE) Alone or in Combination with Ruxolitinib in COVID-19 Positive Patients with PENN Grade 2, 3, 4 Cytokine Released Syndrome (CRS)

Study Population

COVID-19 positive patients with PENN grade 2, 3, 4 CRS and respiratory failure.

Eligibility

Inclusion:

1. Patients positive for COVID-19 by PCR or alternative accepted methodology
2. PENN class 2,3,4 CRS¹⁰
3. Respiratory insufficiency with supplemental oxygen to maintain O2 sat greater than 89%
4. Clinically positive imaging by CXR or CT scan with evidence of bilateral pulmonary infiltrates, ground glass opacification or other pattern of consolidation felt likely to be linked to COVID infection or complication thereof
5. Adults 22 years of age or older

Exclusion:

1. Pregnancy
2. Breast feeding
3. Class 3-4 NYHA heart failure
4. Current use of synthetic disease modifying anti-rheumatic drugs (DMARDs), with the exception of hydroxychloroquine, or IL-6 inhibitors or other immunosuppressive therapies outside of number five below
5. Current use of chronic corticosteroids if in excess of prednisone 10mg per day or equivalent
6. Suspected or confirmed clinically significant bacterial infection
7. History of TB
8. History of HIV
9. History of IBD
10. JAK inhibitor use within last 30 days
11. Creatinine clearance less than 15 ml / min
12. Absolute neutrophil count < 1000
13. Platelet count < 50,000
14. AST or ALT > 5 times the upper limit of normal
15. Clinical assessment that TPE or ruxolitinib could pose unacceptable risk by study participation or the treatment is deemed inappropriate by a study investigator
16. Current enrollment on another investigational protocol for COVID-19 induced CRS

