- The patient is found to be pregnant or intends to become pregnant
- The patient is noncompliant with the study requirements your disease worsens

Data Handling and Recordkeeping

The principal investigator will carefully monitor study procedures to protect the safety of research subjects, the quality of data, and the integrity of the study. All study subject material will be assigned a unique identifying code or number. The key to the code will be kept in a locked file in the Research Division of the Prisma Health Cancer Institute.

Data Collection, Analysis and Outcomes

REDCap EDC software will be used for data management and future statistical analysis. Designated Cancer Institute research staff will perform extraction of patient records.

Overall Response Rate (ORR) will be defined as $\geq 33\%$ decrease in the cytokine load from peak value through study day 14 in one-third or more participants.

Ethical Considerations

This study will be conducted in accordance will all applicable government regulations and Prisma Health research policies and procedures. This protocol and any amendments will be

submitted and approved by the Prisma Health Institutional Review Board (IRB) prior to any study activity.

All study participants will provide informed consent allowing for their tissue and de-identified clinical information to be used for research purposes.

Safety Monitoring and Reporting

A Drug Safety Monitoring Board (DSMB) will be established consisting of a hematologist, pulmonologist and infectious disease specialist not associated with the research team for this investigation. The committee will review all serious adverse events within 48 hours and will review all patient outcomes for cohort 1a before proceeding to enrollment of cohort 1b.

Adverse Events

Adverse events (AEs) are defined as an unexpected medical problem that happens during treatment with a drug or other therapy. The NCI Common terminology criteria for adverse events (CTCAE Version 5.0) will be used as the standardized severity grading system. AEs will also be reported by degree of relatedness as not related, possibly related, likely related or related to the study drug or study therapy.

SAE Reporting to Incyte

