Standard statistical methods will be employed to analyze all data. It is anticipated that the following techniques may be used: descriptive statistics, t-test, Chi-square, Fisher’s exact test, Kaplan-Meier analysis, and graphical displays. This protocol may not reflect all analyses planned for the study; additional analyses may be conducted for observational purposes only.

Summary statistics will consist of numbers and percents of responses in each category for discrete measures, and of mean, n, standard deviation, median, minimum, maximum and 95% confidence intervals for continuous measures.

Sample Size Determination

The initial sample size is 20. Each cohort will enroll 10 patients. This number is considered sufficient for an exploratory pilot study to provide information for planning further investigations.

Analysis of Safety

The safety evaluation will compare the proportion of Subjects in each treatment group who exhibit treatment-related adverse effects. These adverse events will be presented for individual patients as a listing of events.

Dissemination of Results

Results of this study may be used for presentations, posters, publications, or extramural grant applications. The publication will not contain any identifiable information that could be linked to a study patient.

References

<https://doi.org/10.1038/s41586-020-2012-7>
2. World Health Organization. Novel coronavirus situation report-2. January 22, 2020.
<https://www.who.int/docs/default-source/coronavirus/situation-reports/20200122-sitrep-2-2019-ncov.pdf> (Accessed on April 7, 2020).
3. P. Conti, G. Ronconi, A. Caraffa, C. Gallenga, R. Ross, I. Frydas, S. Kritas. Induction of pro-inflammatory cytokines (IL-1 and IL-6) and lung inflammation by COVID-19: anti-inflammatory strategies. *J Biol Regul Homeost Agents*. 2020 Mar 14; 34(2).
4. Puja Mehta, Daniel F McAuley, Michael Brown, Emilie Sanchez, Rachel S Tattersall, Jessica J Manson. COVID-19: consider cytokine storm syndromes and immunosuppression. *The Lancet*. 28 March–3 April 2020.

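### The only stated efficacy criterion for primary endpoint 1 reduces each patient's fall in cytokine load to yes/no at 33%, and no continuous measure of the reduction is tied to that endpoint

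*Combined protocol and SAP*

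**What the plan says.** - **Primary Endpoints, item 1:** "To document the efficacy of TPE alone or in conjunction with ruxolitinib in decreasing the cytokine load over a 14-day intervention study". No cut-off and no test is attached.
- **Data Collection, Analysis and Outcomes:** the Overall Response Rate (ORR) is a fall of at least 33%, described as a "decrease in the cytokine load from peak value through study day 14 in one-third or more participants". This is the only numerical efficacy criterion in the document. No reason is given for 33%.
- **General Statistical Considerations:** the techniques that may be used are "descriptive statistics, t-test, Chi-square, Fisher’s exact test, Kaplan-Meier analysis, and graphical displays", none assigned to an endpoint. Discrete measures are summarised as "numbers and percents of responses in each category for discrete measures". Continuous measures get mean, SD, median, range and 95% CI.
- **Secondary Endpoints:** item 1 relates clinical course to how far specific cytokines fall. Item 5 maps CRP, ferritin and six cytokines over the study.
- **Schedule of Assessments and Appendix B:** cytokines are drawn daily, with a repeat after each exchange.
- **Sample Size Determination:** "The initial sample size is 20. Each cohort will enroll 10 patients". The justification is: "This number is considered sufficient for an exploratory pilot study to provide information for planning further investigations".
- **Study Design:** "Two sequential cohorts, 10 patients per cohort", open label. The background section hypothesises that "concomitant suppression of production will produce superior amelioration of the cytokine load".

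**The concern.** The criterion cuts twice: first each patient at 33%, then the group at one-third. Falls of 34% and 95% score the same, and so do falls of 0% and 32%. The result is a count, which says nothing about how large the typical reduction was or how much it varied between patients. A later trial would need those two figures for its sample size, and planning further work is the stated reason for enrolling 20 patients.

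The cut also bears on the combination hypothesis. If most patients on exchange alone already pass 33%, a deeper fall with ruxolitinib added could not show in the responder count.

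The issue holds whichever sample serves as the reference, and wherever the one-third bar is set.

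**Working it through.** The plan states no power, effect size, SD or expected response rate, so it has no figure to reproduce. The only input from the document is 10 patients per cohort. The rest is assumed for illustration: log change is normal with equal SD in both cohorts, and tests are two-sided at 5%.

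**Step 1. Precision of the count.** With 4 of 10 responding, the exact 95% CI is 12% to 74%. With 7 of 10 it is 35% to 93%.

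**Step 2. Information kept by the cut.** For response rate p with normal quantile z, the large-sample efficiency relative to the normal mean is φ(z)² / [p(1 − p)].

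| p | φ(z) | Efficiency | 10 patients count as |
|---|---|---|---|
| 1/3 | 0.364 | 0.595 | 5.9 |
| 1/2 | 0.399 | 0.637 (maximum) | 6.4 |
| 0.7 | 0.348 | 0.576 | 5.8 |
| 0.9 | 0.175 | 0.342 | 3.4 |

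This is an asymptotic result applied to 10 patients, so it is indicative only.

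**Step 3. A hypothetical cohort contrast, 10 v 10.** Put cohort 1A at one-third responding (a convenient reference, not a rate the plan expects) and cohort 1B at 60, 70, 80 or 90%. The shift in SD units is d = z(p₂) − z(p₁); for 60%, d = 0.253 + 0.431 = 0.68. The t-test has 18 df and noncentrality d√(10/2), which gives 1.53, 2.14, 2.85 and 3.83. Power for the binary tests comes from enumerating all 121 outcomes; the Boschloo region has maximum size 4.22%.

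| Cohort 1B response | 60% | 70% | 80% | 90% |
|---|---|---|---|---|
| d | 0.68 | 0.96 | 1.27 | 1.71 |
| Fisher, % | 9.5 | 19.7 | 36.3 | 60.3 |
| Boschloo, % | 20.2 | 35.7 | 55.5 | 77.3 |
| t-test on log change, % | 30.5 | 52.4 | 76.8 | 95.1 |
| t-test minus Boschloo, points | 10.3 | 16.7 | 21.3 | 17.8 |
| t-test minus Fisher, points | 21.0 | 32.7 | 40.5 | 34.8 |
| Wilcoxon, t with 4 df, % | 23.7 | 40.9 | 64.5 | 88.8 |
| Wilcoxon minus Boschloo, points | 3.5 | 5.2 | 9.0 | 11.5 |

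The Wilcoxon row is from 10,000 simulated trials, with the shift set to give the same response rates under the heavier-tailed distribution.

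**Step 4. Sensitivity to the assumed rates.** With cohort 1A at 50% and 1B at 80% or 90%, Boschloo gives 25.4% and 47.1%, and the t-test 42.9% and 77.3%: gains of 17.5 and 30.2 points. At d = 0.5 with 1A at one-third, the normal approximation gives 20.0% for the continuous comparison against 13.5% for the binary one, a gain of 6.5 points. The ranges in step 3 are therefore not bounds. The t-test itself needs d of about 1.32 for 80% power.

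**The case against.** The strongest reply is that the plan does not confine itself to a count. Levels are collected daily, continuous summaries and a t-test are listed, and the secondary endpoints use the degree of reduction and the course of cytokine levels. A reader might infer from the ORR that the continuous information is thrown away. The documents do not support that: the data are kept and can be analysed. Nor is the ORR called the primary analysis. What remains is that nothing links a continuous measure of change to primary endpoint 1, while one binary criterion is spelled out. A generic list of techniques that may be used does not fill that gap.

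A reader might also infer that the plan's comparison of cohorts loses a definite amount of power, or that a fixed 40% or so of the information is lost. Neither is supported. No efficacy contrast between cohorts is specified; the only comparison between groups is for safety. The cohorts are sequential and unmasked, and the study is a hypothesis-generating pilot. Every power figure rests on assumed rates and distribution, Boschloo's test is not on the plan's list, and power is low either way for moderate effects. This objection stands against the power figures, but it leaves the within-cohort estimation point untouched.

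Finally, a log ratio cannot be computed from the plan as it stands. Cytokine load across six analytes is not defined, and the window through day 14 could mean the day-14 value, the lowest value or any day. A responder rule can count a patient who dies or withdraws as a non-responder, whereas a log ratio needs a stated rule. This stands, and the fix has to cover it.

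**Conclusion.** The concern holds as a gap in how primary endpoint 1 is measured. Its one stated criterion is a twice-dichotomised count with no rationale for the 33% cut, and it yields neither the mean reduction nor the between-patient SD. That conclusion needs no distributional assumption.

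The size of the loss is illustrative. Under a normal log change, the cut keeps at most about 64% of the information, and less as the response rate moves away from 50%. The power gains of about 10-21 points over Boschloo and 21-41 over Fisher apply only to an exploratory contrast that the plan does not contain, under the rates assumed above. With heavier tails, the Wilcoxon gain over Boschloo is 3.5 to 11.5 points. The change should be made because it serves the pilot's stated purpose using data already collected.

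**What to change.** In Data Collection, Analysis and Outcomes:

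1. Make the per-patient log ratio of cytokine load the main measure for primary endpoint 1. Name the later sample and the reference sample, and say whether the ratio is per cytokine or for a named composite.
2. Report it per cohort as a geometric mean percent reduction with 95% CI, together with the between-patient SD of the log ratio.
3. State how deaths, missing later samples and values below the detection limit are handled.
4. Label any cohort contrast exploratory: t-test on the log ratio, with the Wilcoxon test as a sensitivity analysis.
5. Keep the responder rate at 33% or more as a secondary descriptive summary.

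The cost is a short addition to the analysis text, with no new samples, visits or patients. The headline becomes less simple than a response rate. The sponsor must also settle the load measure, the later sample, and the rules for missing and undetectable values, preferably before the data are seen.

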17. Stage 4 obstructive lung disease with chronic hypoxic respiratory failure requiring supplemental O2 at baseline, or ILD with chronic hypoxic respiratory failure requiring supplemental O2 at baseline

Treatment Plan

Device: Spectra Optia Apheresis System

Intended Use of Device: Therapeutic Plasma Exchange performed per marketed labeling

Drug: Ruxolitinib (generic) marketed as brand name, Jakafi ,manufactured by Incyte Corporation, will be used per the marketed package insert.

Cohort 1A: TPE, five single plasma volume exchanges over 7 days (every day x 2 then every other day x 3) with albumin or FFP replacement if underlying coagulopathy per institutional protocol (Appendix A).

Other – standard medical care

Cohort 1B: TPE as in cohort 1A combined with ruxolitinib 5mg po BID beginning day prior to first TPE and continuing BID for total of 14 days. On days of TPE, ruxolitinib dosing will be immediately post procedure and a second dose approximately 8 hours later.

Other – standard medical care

Schedule of Assessments

Pre Treatment

Standard of Care Assessments

- Complete Blood Count (CBC)
- Comprehensive Metabolic Panel (CMP)
- C-Reactive Protein (CRP)
- Ferritin
- lipid panel
- Hepatitis B Surface Antigen, Hepatitis B Surface Antibody, Hepatitis B Core Antibody and Hepatitis C Antibody
- PT/INR
- Partial Thromboplastin Time (PTT)
- Fibrinogen
- type and screen
- serum pregnancy test
- physical examination

Study Related Assessments

- cytokine panel
- peripheral blood for biorepository
- peripheral blood for pharmacogenomics

During Treatment (On Study)

Standard of Care Assessments

- daily CBC
- daily CRP
- PaO₂/FiO₂ ratios days (with ABGs) per Appendix B
- amount of supplemental O₂, SPO₂%, respiratory rate, imaging per MD discretion (*for non-intubated patients*)
- measure daily SPO₂%, FiO₂; PEEP; and lung compliance (inspiratory pause – V_t/P_{plat} – PEEP) or plateau pressures (*mechanically vented patients*)
- daily Basic Metabolic Panel (BMP)
- physical examination

Study Related Assessments

- daily collection of study related adverse events and/or serious adverse events
- Fibrinogen (on days of TPE only)
- daily cytokine panel and GM-CSF
- repeat cytokine panel and GM-CSF within 60 minutes post TPE (on days of procedure only)
- serum ferritin per Appendix B
- peripheral blood and plasma waste for biorepository per Appendix B
- day 28 office visit or virtual health visit to assess clinical status of the patient

Risk Analysis

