The proposed patient population is not anticipated to be at an increased risk compared to a clinically similar population without COVID-19 infection. The device and drug will be used as marketed. Standard risks for the device and drug are outlined in the patient informed consent document. Risks will be minimized by conducting the trial in the inpatient setting of an acute care hospital with dedicated and trained therapeutic apheresis staff, licensed medical personnel and experienced research team members under the direction and oversight of the principal investigator. In the event of patient status improvement, discharge will be acceptable after completion of therapeutic plasma exchange. Daily outpatient follow-up through patient completion of study required assessments will occur in a dedicated phase I research unit.

Removal of medications with TPE is a risk. However, consultation with a hospital pharmacist will occur as needed to determine if a change in timing of medication administration is needed or if medication reloading should occur post TPE.

Dose Modifications

The starting dose of ruxolitinib is 5mg po bid. The need for dose adjustments will be assessed on a daily basis by the research team and pharmacist.

- AST/ALT > 5x ULN, reduce dose of ruxolitinib to 5mg po once daily¹¹
- Platelet count between 25,000 and 35,000, reduce dose of ruxolitinib to 5mg po once daily. Platelet count < 25,000, hold ruxolitinib. May resume once platelet count >25,000 with dosing based on actual platelet count.
- Absolute neutrophil count < 500, hold ruxolitinib until > 500 then resume at full dose
- Creatinine Clearance <15ml/min, discontinue ruxolitinib

Duration of Investigations

A six month patient recruitment period is anticipated. Patient participation is 15 days in duration. An additional six month period of data analysis is anticipated for an overall period of investigation equaling 12 months

Treatment Discontinuation

Treatment discontinuation will occur under the following conditions:

- The patient withdraws consent either from treatment or from the study
- The patient is lost to follow-up
- The patient experiences a side effect that per the protocol requires treatment to end
- The physician deems treatment discontinuation is in the best interest of the patient
- The patient is found to be eligible to participate in the study after being enrolled and continued treatment in this study is not in the best interest of the patient

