APPENDIX A:**TPE-Plasma Therapy Plan**

Apheresis Orders	Frequency

 Therapeutic Plasma Apheresis with Plasma Replacement 	As Ordered
IV Access	

 Initiate peripheral IV Protocol 	Daily

 Access Central Venous Catheter 	Daily

 Access A/V Fistula for Procedure 	Daily
Pre-Procedure Labs (Baseline)	

 CBC with Differential 	Once

 CMP 	Once

 LDH 	Once

 Haptoglobin 	Once

 PT/INR 	Once

 PTT 	Once

 Reticulocyte Count 	Once

 ADAM TS 13 Activity 	Once

 Type and Screen 	Once

 Bilirubin Total and Direct 	Once

 Prepare Plasma 	Once
Labs	

 CBC with Differential 	Daily

 CMP 	Daily

 LDH 	Daily

 Haptoglobin 	Daily
Anticoagulant Prime	

 Anticoagulant citrate dextrose injection 500 ml 	PRN
Medications	

 diphenhydramine (Benadryl) 25 mg IV 	Once

 calcium gluconate 3g in NS 250ml IV 	Once

 calcium gluconate 3g in NS 250ml IV 	PRN

 calcium carbonate tablet 1500 mg PO 	PRN

 alteplase 2mg in 10ml syringe 	PRN clot clearance
Hypersensitivity Regimen	

 at any sign of anaphylaxis, stop infusion, notify MD and administered prescribed medications 	PRN

 diphenhydramine (Benadryl) 50 mg IV 	PRN

 methyleprednisolone (Solu-Medrol) 40 mg IV 	PRN

 famotidine (Pepcid) 20 mg IV 	PRN
Nursing Orders	

 Transfuse Plasma 	Once

TPE-Albumin Therapy Plan

Apheresis Orders	Frequency

 • Therapeutic Plasma Apheresis with Albumin Replacement 	As Ordered
IV Access	

 • Initiate peripheral IV Protocol 	Daily

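### The only AE definition is limited to unexpected problems, but primary endpoint 2 covers all therapy-related AEs

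*Combined protocol and SAP*

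**What the plan says.** The second item under Primary Endpoints is "Analysis of all therapy related adverse events (AEs". Under Analysis of Safety, the evaluation is to "compare the proportion of Subjects in each treatment group who exhibit treatment-related adverse effects", with a listing of events for individual patients. Neither section mentions expectedness.

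The term is defined once, under Adverse Events: "Adverse events (AEs) are defined as an unexpected medical problem that happens during treatment with a drug or other therapy". The same paragraph adds that CTCAE version 5.0 "will be used as the standardized severity grading system". It is not cited as the source of what qualifies as an event. AEs are then to be reported in four classes of relatedness, the lowest of which is for unrelated events.

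Other sections show that many toxicities are foreseen:

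- Risk Analysis: "Standard risks for the device and drug are outlined in the patient informed consent document".
- Dose Modifications: rules triggered by AST/ALT, neutrophil and platelet values, for example "Platelet count < 25,000, hold ruxolitinib".
- Appendix A: both the plasma and the albumin plan carry a hypersensitivity regimen, with the instruction "at any sign of anaphylaxis, stop infusion, notify MD and administered prescribed medications".

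The Schedule of Assessments, under On Study and the subheading Study Related Assessments, lists "daily collection of study related adverse events and/or serious adverse events". SAE Reporting to Incyte requires every SAE to be reported whatever the investigator's view of causality. Safety Monitoring and Reporting has the DSMB review all SAEs.

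**The concern.** A definition decides what enters the database. If staff apply this one as written, a non-serious thrombocytopenia, transaminase rise or mild procedural reaction is a known risk. It is therefore not unexpected, and need not be recorded as an AE. Those are the events one would most expect from an apheresis procedure and a JAK inhibitor, and one of the two primary endpoints is meant to describe them.

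At stake is an understated related-AE rate in a pilot whose stated purpose, under Sample Size Determination, is to inform planning of later studies. Two staff members could also classify the same event differently and both be following the protocol.

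**Working it through.** The plan gives no AE rate, so there is no figure of its own to reproduce. The check is a comparison of sections, followed by the arithmetic of leaving patients out.

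**Step 1: which events are at issue.** An event escapes the count if it is therapy-related, foreseen and non-serious.

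| Event | Where the protocol foresees it | Meets the literal definition? | Within endpoint 2 as worded? |
|---|---|---|---|
| Low platelets or neutrophils, raised AST/ALT | Dose Modifications | No | Yes, if therapy-related |
| Hypersensitivity during TPE | Appendix A, both plans | No | Yes, if therapy-related |
| Other standard device and drug risks | Risk Analysis, by reference to the consent document | No | Yes, if therapy-related |
| Any SAE | SAE Reporting to Incyte | Captured separately | Captured separately |

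The two right-hand columns disagree in the first three rows. No other section supplies a wider definition.

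**Step 2: effect on one cohort's rate.** With n = 10 (Sample Size Determination), each patient whose only related events are foreseen and non-serious moves the rate by 1/10 = 10 percentage points. Exact (Clopper-Pearson) 95% limits are the Beta quantiles B(0.025; x, n−x+1) and B(0.975; x+1, n−x). The counts below are assumptions.

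| Assumed true count | Patients left out | Reported | Exact 95% CI, % |
|---|---|---|---|
| 5/10 | 0 | 5/10 | 18.7 to 81.3 |
| 5/10 | 1 | 4/10 | 12.2 to 73.8 |
| 5/10 | 2 | 3/10 | 6.7 to 65.2 |
| 5/10 | 3 | 2/10 | 2.5 to 55.6 |
| 3/10 | 3 | 0/10 | 0 to 30.8 |

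**Step 3: effect on the cohort difference.** Let a and b be the numbers of patients left out of cohorts 1A and 1B. In percentage points, reported difference (1B minus 1A) = true difference − 10 × (b − a). Assume true counts of 2/10 in 1A and 6/10 in 1B, a difference of 40 points. The Newcombe limits, with Wilson limits l and u for each cohort, are d − √[(p_B − l_B)² + (u_A − p_A)²] and d + √[(u_B − p_B)² + (p_A − l_A)²].

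- None left out: Wilson limits are 0.313 to 0.832 (1B) and 0.057 to 0.510 (1A). The difference is 40 points, 95% CI −2.3 to 67.3.
- Two left out of 1B only: 4/10 vs 2/10, 40 − 20 = 20 points (−18.7 to 52.1).
- Two left out of each: 4/10 vs 0/10, 40 − 0 = 40 points. Wilson limits are 0.168 to 0.687 and 0 to 0.278, giving 3.8 to 68.7. The difference is unchanged, but the interval now excludes zero.
- Two left out of 1A only: 6/10 vs 0/10, 40 + 20 = 60 points.

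The difference can therefore shrink, stay the same or grow. Both cohorts undergo TPE, so procedural reactions can be left out of either. Ruxolitinib toxicity can be left out of 1B only.

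**The case against.** The best defence is that the protocol gives no means of applying the restriction. It has no list of expected events for AE classification, no reference document for expectedness and no step at which expectedness is judged. AEs are sorted by severity and relatedness only. The endpoint says all, and the safety analysis sets no limit. On this view the sentence is a lay description that happens to contain one restrictive word. Much of that stands. The mismatch in wording is certain; an actual undercount is not. A reader might infer that the plan orders foreseen toxicities to be excluded. The documents do not support that: they permit the omission without requiring it. Still, the defence asks staff to set aside the only definition they have been given.

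A second defence is that missed events could be recovered later. Platelet falls could be re-read from the daily CBC, and treated reactions would partly survive in the patient records. That reduces the loss, but abnormal values found afterwards do not come with a relatedness judgement made at the time.

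A reader might also take the daily collection line as a causality filter, so that unrelated non-serious events are discarded before recording. That is too strong. The line stands under the subheading Study Related Assessments, where the phrase can simply mean done for the study. The reporting class for unrelated events supports that milder reading. What remains is an ambiguity to clarify.

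**Conclusion.** The point holds as an inconsistency between the AE definition and primary endpoint 2, and it should be corrected. Applied literally, the definition lowers a cohort's related-AE rate by 10 percentage points for each patient whose only related events are foreseen and non-serious. How many such patients there would be cannot be derived from the documents, and every count in the illustrations is assumed.

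It is tempting to conclude that the definition would hide ruxolitinib toxicity and so shrink the difference between cohorts. That holds only if more patients are left out of 1B than of 1A, which the documents do not establish, so the direction of the effect is unknown. Nor should the point be extended to SAEs, which are reported under their own rule. The ambiguity in the collection line is minor and adds no weight to the main point.

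**What to change.** Under Adverse Events, delete the word unexpected and define an AE as any untoward medical occurrence during study treatment, whether or not expected or related. Keep CTCAE v5.0 for grading. Use the same term under Primary Endpoints, Schedule of Assessments, Adverse Events and Analysis of Safety, where the text now moves between adverse events and adverse effects.

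As a minor clarification, reword the daily collection line in one of two ways. Either drop the study-related qualifier, so that all AEs and SAEs are collected and relatedness is assigned after recording, or state that the class for unrelated events applies to SAEs only. Either is defensible in a 20-patient exploratory pilot. The first means more data entry in a severely ill population; the second means less work but leaves no record of unrelated non-serious events.

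The cost is a wording change in a few places, somewhat higher reported AE rates and, under the first option, some extra data entry for 20 patients. No new visits or tests are needed.
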